7.1.7. Additional Analysis of Adverse Events

7.1.7.1. Dose Limiting Toxicity

A listing of the DLT AEs will be provided by study group and cohort including cohort number with dose level, subject identification, DLT term from investigator as well as CTCAE term and associated severity grade, if available.

7.1.7.2. Treatment-Emergent Adverse Events (TEAE) of Interest

The treatment-emergent AEs of interest (AEI) include:

- Decreased Platelets (Preferred terms are defined in Appendix 2 of this SAP)
- Haemorrhage (Preferred terms are defined in Appendix 3 of this SAP)
- Diarrhoea (Preferred terms are defined in Appendix 4 of this SAP)

The AEIs will be summarized similarly to TEAE by study group and dose level cohort.

7.2. Laboratory Evaluations

Laboratory data collected during the study will be analyzed and summarized using both quantitative and qualitative methods. Summaries of laboratory data will be provided for the FAS and will include data collected up to the last dose of study drug plus 30 days for subjects who have permanently discontinued study drug. The analysis will be based on values reported in conventional units. When values are below the LOQ, they will be listed as such, and the closest imputed value will be used for the purpose of calculating summary statistics as specified in Section 3.7.

A by-subject listing for laboratory test results will be provided by subject ID number and visit in chronological order for hematology, serum chemistry, coagulation, and urinalysis separately. Values falling outside of the relevant reference range and/or having a severity grade of 1 or higher on the CTCAE severity grade will be flagged in the data listings, as appropriate.

No formal statistical testing is planned.

7.2.1. Summaries of Numeric Laboratory Results

Descriptive statistics will be provided by study group and dose level for each laboratory test specified in the study protocol as follows:

- Baseline values
- Values at each postbaseline visit
- Change from baseline at each postbaseline visit

A baseline laboratory value will be defined as the last measurement obtained on or prior to the date/time of first dose of study drug. Change from baseline to a postbaseline visit will be defined as the visit value minus the baseline value. The mean, median, Q1, Q3, minimum, and maximum values will be displayed to the reported number of digits; StD values will be displayed to the reported number of digits plus 1.

In the case of multiple values in an analysis window, data will be selected for analysis as described in Section 3.8.3.

7.2.2. Graded Laboratory Values

The CTCAE, Version 4.03, will be used to assign toxicity grades (0 to 4) to laboratory results for analysis. Grade 0 includes all values that do not meet the criteria for an abnormality of at least Grade 1. For laboratory tests with criteria for both increased and decreased levels, analyses for each direction (ie, increased, decreased) will be presented separately. Local labs will be graded based on central lab normal ranges with in-house macro. In the event that both central and local lab results are collected in the clinical database, the worst toxicity grade will be used for the summary of lab toxicities. All central and local laboratory values will be listed.

7.2.2.1. Treatment-Emergent Laboratory Abnormalities

Treatment-emergent laboratory abnormalities are defined as values that increase at least 1 toxicity grade from baseline at any postbaseline time point, up to and including the date of last dose of study drug plus 30 days for subjects who permanently discontinued study drug, or the last available date in the database snapshot for subjects who were still on treatment at the time of an interim analysis. If the relevant baseline laboratory value is missing, any abnormality of at least Grade 1 observed within the time frame specified above will be considered treatment emergent.

7.2.2.2. Summaries of Laboratory Abnormalities

Laboratory data that are categorical will be summarized using the number and percentage of subjects in the study with the given response at baseline and each scheduled postbaseline visit.

The following summaries (number and percentage of subjects) for treatment-emergent laboratory abnormalities will be provided by lab test, dose level, and study group; subjects will be categorized according to the most severe postbaseline abnormality grade for a given lab test:

- Graded laboratory abnormalities

For all summaries of laboratory abnormalities, the denominator is the number of subjects in the FAS.

A by-subject listing of treatment-emergent laboratory abnormalities will be provided by subject ID number and visit in chronological order. This listing will include all test results that were collected throughout the study for the lab test of interest, with all applicable severity grades displayed.

7.2.3. Liver-related Laboratory Evaluations

Liver-related abnormalities after initial study drug dosing will be examined and summarized using the number and percentage of subjects who were reported to have the following laboratory test values for postbaseline measurements:

- Aspartate aminotransferase (AST): (a) > 3 times of the upper limit of reference range (ULN); (b) > 5 x ULN; (c) > 10 x ULN; (d) > 20 x ULN
- Alanine aminotransferase (ALT): (a) > 3 x ULN; (b) > 5 x ULN; (c) > 10 x ULN; (d) > 20 x ULN
- AST or ALT: (a) > 3 x ULN; (b) > 5 x ULN; (c) > 10 x ULN; (d) > 20 x ULN
- Total bilirubin: (a) > 1 x ULN; (b) > 2 x ULN
- Alkaline phosphatase (ALP) > 1.5 x ULN
- AST or ALT > 3 x ULN: (a) total bilirubin > 1.5 x ULN; (b) total bilirubin > 2 x ULN; (c) total bilirubin > 2 x ULN and ALP < 2 x ULN

The summary will include data from all postbaseline visits up to 30 days after the last dose of study drug. For individual laboratory tests, subjects will be counted once based on the most severe postbaseline values. For both the composite endpoint of AST or ALT and total bilirubin, subjects will be counted once when the criteria are met at the same postbaseline visit date. The denominator is the number of subjects in the FAS who have nonmissing postbaseline values of all relevant tests at the same postbaseline visit date.

In addition, a listing of subjects who met at least 1 of the above criteria will be provided.

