- 8) Adequate organ function defined as follows:
 - a. Hematologic: Platelets $\geq 100 \times 10^9/L$; Hemoglobin ≥ 9.0 g/dL; ANC $\geq 1.5 \times 10^9/L$ (without platelet transfusion or any growth factors within previous 7 days of the hematologic laboratory values obtained at screening visit). Patients in the Group 3 lymphoma expansion may be enrolled with an ANC of $\geq 1.0 \times 10^9/L$; Platelets $\geq 75 \times 10^9/L$.
 - b. Hepatic: Aspartate transaminase (AST) / Alanine transaminase (ALT) ≤ 2.5 x upper limit of normal (ULN) (if liver metastases are present, ≤ 5 x ULN); Total or conjugated bilirubin ≤ 1.5 x ULN
 - c. Renal: Serum Creatinine ≤ 1.5 x ULN or creatinine clearance (CrCl) ≥ 60 ml/min as calculated by the Cockcroft-Gault method
- 9) Coagulation: International Normalized Ratio (INR) ≤ 1.2
- 10) Negative serum pregnancy test for female subjects ([Appendix 7](#))
- 11) Male subjects and female subjects of childbearing potential who engage in heterosexual intercourse must agree to use protocol specified method(s) of contraception as described in [Appendix 7](#).
- 12) Females who are nursing must agree to discontinue nursing before the first dose of GS-5829
- 13) Able and willing to provide written informed consent to participate in the study

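### SAP 7.2.3 counts post-dose liver values over fixed ULN multiples without regard to baseline, although eligible subjects can enter above 5 of its 18 cut-offs (9 on one reading of the bilirubin criterion)

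*SAP*

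**What the plan says.** SAP 7.2.3 opens: "Liver-related abnormalities after initial study drug dosing will be examined and summarized using the number and percentage of subjects", meaning those "who were reported to have the following laboratory test values for postbaseline measurements". The rows include "AST or ALT: (a) > 3 x ULN; (b) > 5 x ULN; (c) > 10 x ULN; (d) > 20 x ULN", with the same four multiples for AST alone and for ALT alone. Then come "Total bilirubin: (a) > 1 x ULN; (b) > 2 x ULN", "Alkaline phosphatase (ALP) > 1.5 x ULN", and three composites that pair AST or ALT above 3 x ULN with total bilirubin above 1.5 x ULN, above 2 x ULN, or above 2 x ULN with ALP below 2 x ULN. That makes 18 cut-offs.

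The counting rule is: "For individual laboratory tests, subjects will be counted once based on the most severe postbaseline values". Composites must be met on a single post-baseline visit date. The denominator is FAS subjects with the relevant post-baseline results. Baseline enters neither the count, nor the denominator, nor the supporting listing.

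Protocol 4.2, criterion 8b, caps AST/ALT at 2.5 x ULN, raised to 5 x ULN "if liver metastases are present". The bilirubin limit of 1.5 x ULN applies to "Total or conjugated bilirubin". Sections 4.2 and 4.3 set no ALP limit.

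Elsewhere the plan does use baseline. Protocol 8.6.3 puts the emphasis of laboratory reporting on treatment-emergent abnormalities, SAP 7.2.2.1 requires a rise of at least one grade, and SAP 7.2.4 gives shift tables by grade.

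**The concern.** A subject who enters above a cut-off and whose value never moves is counted in a table presented as abnormalities after dosing. In a population where liver and bone metastases are to be expected, such a row mixes disease present at entry with anything that arose on treatment, and the reader of the table cannot separate the two.

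Safety and tolerability are primary objectives, and dose-level cells are small. One carried-over elevation can therefore change a row's percentage visibly. The rows most exposed are those that no other planned summary sets against baseline.

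**Working it through.** The plan states no figure here to reproduce. The check compares each cut-off with the highest value that the eligibility criteria allow, then asks whether another planned summary supplies the baseline comparison.

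**Step 1. Cut-offs that an eligible entry value can exceed**

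| Rows in SAP 7.2.3 | Cut-offs (x ULN) | Highest eligible entry value (x ULN) | Exceedable at entry |
|---|---|---|---|
| AST | 3, 5, 10, 20 | 5 with liver metastases, 2.5 without | > 3, with metastases only |
| ALT | 3, 5, 10, 20 | same | > 3, with metastases only |
| AST or ALT | 3, 5, 10, 20 | same | > 3, with metastases only |
| Total bilirubin | 1, 2 | 1.5 if total is capped; no limit if conjugated alone suffices | > 1; also > 2 if uncapped |
| ALP | 1.5 | no limit | yes |
| Three composites | AST or ALT > 3 with bilirubin > 1.5 or > 2 | as above | none if capped; all three with metastases if uncapped |

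Counts out of 4 + 4 + 4 + 2 + 1 + 3 = 18:

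- Total bilirubin capped, liver metastases: 3 + 1 + 1 = 5.
- Total bilirubin capped, no liver metastases: 1 + 1 = 2.
- Total bilirubin uncapped, liver metastases: 5 + 1 + 3 = 9.
- Total bilirubin uncapped, no liver metastases: 2 + 1 = 3.

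No eligible entry value meets the > 5, > 10 or > 20 x ULN transaminase rows. These counts concern the eligibility value. Protocol 6.1.13 takes that value within 7 days before Day 1, chemistry is repeated at C1D1 (Appendix 2), and SAP 7.2.1 defines baseline as the last value on or before first dose. The analysis baseline can therefore differ from it.

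**Step 2. Baseline-adjusted coverage elsewhere**

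Protocol Table 6-2 gives grade boundaries for AST/ALT at 3 and 5 x ULN and for bilirubin at 1.5 and 3 x ULN.

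- AST or ALT singly, > 3 and > 5: these are grade boundaries, so the shift and treatment-emergent tables cover them.
- AST-or-ALT: separate AST and ALT tables do not give the count of subjects with either.
- Bilirubin > 2: lies inside Grade 2, so not covered.
- Bilirubin > 1: Table 6-2 does not print the lower edge of Grade 1. The shift table covers this row only if Grade 1 starts just above ULN.
- ALP > 1.5: neither document prints an ALP grade boundary, so no coverage at this cut-off is shown. SAP 7.2.1 gives only numeric summaries.
- Composites: no grade table combines tests on the same date.

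**Step 3. Illustration of size**

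One unchanged subject adds 1/6 = 17% in a cohort of 6, or 1/3 = 33% in a cohort of 3.

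More generally, let q be the share who enter above a cut-off and remain above it, and n the new-onset rate among the rest. The planned row shows q + (1 - q) x n. The documents give neither quantity. With assumed n = 5%:

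- q = 5%: 5.0 + 4.75 = 9.75%; carried over, 33 x 0.05 = 1.65 subjects.
- q = 10%: 10.0 + 4.5 = 14.5%; 3.3 subjects.
- q = 20%: 20.0 + 4.0 = 24.0%; 6.6 subjects.

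The 33 is the number enrolled (SAP 1.3). The planned row prints only the sum. A split row would print both terms.

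**The case against.** The strongest defence is that baseline is not lost. SAP 7.2.1 gives baseline, visit values and change for every test. SAP 7.2 lists every result by subject, and 7.2.3 adds a listing of each subject who meets a criterion. With 33 subjects, anyone counted can be looked up. The section says only that values are post-baseline and does not call them treatment-emergent or drug-related. No test is planned, and DLTs have their own definition based on relatedness (Protocol 3.2). All of this stands, and it limits the weight of the point. It does not repair the table, because recovering the split by hand leaves the printed percentages unsplit, and the 7.2.3 listing does not promise baseline values.

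A reader might infer that, because the shift and treatment-emergent tables work by grade, they miss all of these cut-offs. Table 6-2 shows otherwise for AST and ALT taken singly: stable ALT at 4 x ULN is Grade 2 before and after dosing, shows no shift, and is not treatment-emergent.

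A reader might also infer that the composites can simply be met at entry. That depends on letting a conjugated value satisfy the bilirubin limit while total bilirubin is higher. If total bilirubin is capped at 1.5 x ULN, no eligible entry value meets bilirubin > 2 x ULN or any composite. The wording allows either reading.

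**Conclusion.** The concern holds in limited form. SAP 7.2.3 ignores baseline, and eligible subjects with liver metastases can start above 5 of its 18 cut-offs, or 9 on the uncapped bilirubin reading. Without liver metastases the figures are 2 and 3. The uncovered gap is AST-or-ALT, ALP > 1.5 x ULN, bilirubin > 2 x ULN and the composites. Of these, bilirubin > 2 x ULN and the composites can be exceeded by an eligible entry value only on the uncapped reading.

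Three further inferences are not supported. The counts are not false: each counted subject did have the post-baseline value, and the fault is that carried-over and new elevations are pooled. No overcount rate can be stated, since the documents give neither the share with liver metastases nor the distribution of entry values; the percentages in the working are illustrations. Nor do the documents show that carry-over differs by dose level, only that small cells would make one such subject conspicuous if the table is laid out by dose level, as the other laboratory summaries are.

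This is a flaw of presentation in one descriptive safety table, worth correcting because the correction is cheap.

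**What to change.** In SAP 7.2.3, keep the planned all-subject post-baseline count and its FAS-based denominator. For each criterion and each composite, add two counts: subjects who did not meet it at baseline (newly met) and subjects who already met it. Treat a missing baseline as not met, in line with the missing-baseline rule in SAP 7.2.2.1. Keeping one denominator avoids a different base in every row.

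In the supporting listing, show baseline AST, ALT, total bilirubin and ALP, and liver-metastasis status. This also identifies a subject whose stable transaminase elevation already meets half of a composite, so that a later bilirubin rise alone completes it.

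The cost is one extra column split, with small cells. Baseline chemistry is already collected. Liver-metastasis status has to be known to apply criterion 8b, though the documents do not say whether it is a separate data field.

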7.2.4. Shifts Relative to the Baseline Value

Shift tables will be presented by showing change in severity grade from baseline to the worst grade postbaseline.

7.3. Body Weight and Vital Signs

Descriptive statistics will be provided by study group and dose level for body weight and vital signs as follows:

- Baseline value
- Values at each postbaseline visit
- Change from baseline at each postbaseline visit

A baseline value will be defined as the last available value collected on or prior to the date of first dose of study drug. Change from baseline to a postbaseline visit will be defined as the postbaseline value minus the baseline value. Body weight and vital signs measured at unscheduled visits will be included for the baseline value selection.

In the case of multiple values in an analysis window, data will be selected for analysis as described in Section 3.8.3. No formal statistical testing is planned.

A by-subject listing of vital signs will be provided by subject ID number and visit in chronological order. Body weight will be included in the vital signs listing, if space permits. If not, they will be provided separately.

7.4. Prior and Concomitant Medications

Medications collected at screening and during the study will be coded using the current version of the World Health Organization (WHO) Drug dictionary.

7.4.1. Prior Medications

Prior medications are defined as any medications taken before a subject took the first study drug.

A summary of prior medications will not be provided.

7.4.2. Concomitant Medications

Concomitant medications are defined as medications taken while a subject took study drug. Use of concomitant medications will be summarized by preferred name using the number and percentage of subjects for each study group and dose level. A subject reporting the same medication more than once will be counted only once when calculating the number and percentage of subjects who received that medication. The summary will be ordered by preferred term in descending overall frequency. For drugs with the same frequency, sorting will be done alphabetically.

For the purposes of analysis, any medications with a start date prior to or on the first dosing date of study drug and continued to be taken after the first dosing date, or started after the first dosing date but prior to or on the last dosing date of study drug will be considered concomitant medications. Medications started and stopped on the same day as the first dosing date or the last dosing date of study drug will also be considered concomitant. Medications with a stop date prior to the date of first dosing date of study drug or a start date after the last dosing date of study drug will be excluded from the concomitant medication summary. If a partial stop date is entered, any medication with the month and year (if day is missing) or year (if day and month are missing) prior to the date of first study drug administration will be excluded from the concomitant medication summary. If a partial start date is entered, any medication with the month and year (if day is missing) or year (if day and month are missing) after the study drug stop date will be excluded from the concomitant medication summary. Medications with completely missing start and stop dates will be included in the concomitant medication summary, unless otherwise specified. Summaries will be based on the FAS. No formal statistical testing is planned.

All prior and concomitant medications (other than per-protocol study drugs) will be provided in a by-subject listing sorted by subject ID number and administration date in chronological order.

7.5. Electrocardiogram Results

Electrocardiogram (ECG) analysis results are intended to identify meaningful changes in the QT interval. If potential abnormalities of interest are identified, further analyses may be conducted. Summaries of ECG data will be provided for the FAS for each scheduled time point. Both central and local ECG measurements will be considered for analysis. No formal statistical testing is planned.

7.5.1. Corrected QT Intervals

The QT interval (measured in millisecond [msec]) is a measure of the time between the start of the Q wave and the end of the T wave in the heart's electrical cycle. The QT interval represents electrical depolarization and repolarization of the ventricles. The QT interval is affected by heart rate, and a number of methods have been proposed to correct QT for heart rate.

Corrected QT (QTc) intervals will be derived using Fridericia's correction (QTcF) as follows:

$$QTcF = \frac{QT}{\sqrt[3]{RR}}$$

where QT is measured in msec; $RR = 60/\text{Heart Rate (beats per min [bpm])}$ and RR is measured in seconds

The maximum postdose QTcF interval values obtained during the study will be summarized within the following categories:

- ≤ 450 msec
- > 450 msec - ≤ 480 msec
- > 480 msec - ≤ 500 msec
- > 500 msec

The maximum postdose change in QTcF interval values obtained during the study will also be summarized within the following categories:

- ≤ 30 msec
- > 30 msec - ≤ 60 msec
- > 60 msec

The QTcF and uncorrected QT values at each visit and time point and change from baseline at each visit and time point will be summarized for the FAS by study group and dose level using descriptive statistics.

7.5.2. PR and QRS Intervals

The PR interval (measured in msec) is a measure of the time between the start of the P wave (the onset of atrial depolarization) and the beginning of the QRS complex (the onset of ventricular depolarization). The QRS interval measures the duration of the QRS complex. The maximum ventricular rate (VR) and PR and QRS intervals observed during the study will be categorized. The number and percentage of subjects having values in the following ranges will be presented by study group and dose level:

- VR > 100 bpm
- PR interval > 200 msec
- QRS interval > 110 msec

In addition, VR, PR, RR, and QRS values at each visit and time point and change from baseline at each visit and time point will be summarized for the FAS by study group and dose level using descriptive statistics.

7.6. Other Safety Measures

No additional safety measures are specified in the protocol.

7.7. Changes From Protocol-Specified Safety Analyses

There are no deviations from the protocol-specified safety analyses.

8. PHARMACOKINETIC (PK) ANALYSES

8.1. PK Sample Collection

Plasma samples for GS-5829 PK will be collected in cohorts 1 - 3 of Group 1 on Study Day 1 at predose, 0.5, 1, 2, 3, 4, 6, 8, 12, and 24 hours postdose and in cohorts 4 - 6 of Group 1 and all cohorts of Group 2 on Cycle 1 Day 1 at predose, 0.5, 1, 2, 3, 4, 6, 8, 12, and 24 hours postdose. Additional samples will be collected at 48 and 72 hours postdose in cohorts 1 - 3 of Group 1 relative to first dose of GS-5829. Plasma samples for GS-5829 PK will be collected in all cohorts at predose, 0.5, 1, 2, 3, 4, 6, 8, 12, and 24 hours post dose relative to GS-5829 administration on Cycle 1 Day 8. Sparse PK samples will be collected in all cohorts at trough (20 - 26 hours postdose) on Cycle 1 Day 4, 2 - 4 hours post dose on Cycle 1 Day 15, and anytime postdose on Day 1 of Cycles 2 through 6. In one or more cohorts, PK samples will be collected on Day 1 of Cycle 2 at pre-dose and 0.5, 1, 2, 3, 4, 6, 8, and 24 hours post dose.

8.1.1. Estimation of PK Parameters

PK parameters will be estimated using Phoenix WinNonlin[®] software using standard noncompartmental methods. The linear/log trapezoidal rule will be used in conjunction with the appropriate noncompartmental model, with input values for dose level, dosing time, plasma concentration, and corresponding real-time values, based on drug dosing times whenever possible.

All predose sample times before time-zero will be converted to 0.

For area under the curve (AUC), samples BLQ of the bioanalytical assays occurring prior to the achievement of the first quantifiable concentration will be assigned a concentration value of 0 to prevent overestimation of the initial AUC. Samples that are BLQ at all other time points will be treated as missing data in WinNonlin. The nominal time point for a key event or dosing interval (τ) may be used to permit direct calculation of AUC over specific time intervals. The appropriateness of this approach will be assessed by the PK scientist on a profile-by-profile basis.

Pharmacokinetic parameters such as AUC_{τ} , λ_z and $t_{1/2}$ are dependent on an accurate estimation of the terminal elimination phase of drug. The appropriateness of calculating these parameters will be evaluated upon inspection of PK data on a profile-by-profile basis by the PK scientist.

